This is a single-center, prospective, ‘open-label,’ investigator-initiated pilot study evaluating the role of continuous glucose monitor (CGM) use either alone or with remote monitoring capabilities that enable subjects to share CGM data with family and friends (whom we will call “followers” in this protocol) among women with T1DM associated with pregnancy. We hypothesize that CGM use will decrease percentage of glucose values below the target range, decrease frequency of severe hypoglycemic episodes, and increase post-prandial glucose values into the target range, with a possible reduction in A1C compared to not using CGM during pregnancy. We hypothesize that the use of remote technology (**Share™ technology**) with subject’s designated follower will decrease hypoglycemia fear and the frequency of severe hypoglycemic episodes compared to CGM use alone in pregnancy or not using CGM use in pregnancy. This study aims to improve maternal glucose management among women with T1DM with a hope to also improve health outcomes during pregnancy.

The study will enroll up to 40 patients from the Barbara Davis Center for Childhood Diabetes (BDC) Adult clinic over the age of 18 years who are pregnant (13 weeks gestation or less) or plan to become pregnant within the following 6 months. The study will also attempt to enroll up to 40 followers (one per pregnant subject) who are family members or friends of the pregnant subjects and over the age of 18 years. All subjects meeting these criteria will be invited to sign informed consent and participate in the study. All pregnant subjects will be stratified into one of three groups: (1) CGM use alone, (2) CGM use with Share™, (3) no CGM use. CGM use will be offered to all subjects, but individuals who do not want to wear a CGM will be stratified to Group 3. Stratification for Groups 1 and 2 will depend on the following: subjects and followers who have iPhones, iPads, and/or iPod touches will be placed into Group 2 which requires one of these devices to function, while all others will be placed in Group 1. All subjects will be followed for study visits with similar frequency during the pregnancy, and subjects in Groups 1 and 2 will wear the Dexcom G4 Platinum® CGM system from the first pregnancy visit until delivery. All subjects in Group 2 will also use the Share™ technology from the first pregnancy visit until delivery.

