CGM data will be analyzed for mean blood glucose values, time spent in hyperglycemic (>240, >300mg/dl) and hypoglycemic (<50, <70, <80 mg/dl) ranges and various indices of glycemic variability. Laboratory analysis for A1C will be performed at baseline, monthly thereafter during the pregnancy, and post-partum. Routine blood tests will be performed in all subjects in each trimester (see Table 1).

Primary outcomes will be:

- 1) Glucose variability as measured by glucose excursions from self-monitoring blood glucose (SMBG) data through log books and downloads as well as CGM downloads and various indices [J-index, mean amplitude of glycemic excursion (MAGE), high blood glucose index (HBGI), low blood glucose index (LBGI)] from CGM downloads.
- 2) Changes detected by the hypoglycemia fear questionnaire.

Secondary outcomes will be:

- 1) How CGM alone and CGM with Share™ usage affect A1C compared to no CGM use,
- 2) Progression of diabetes complications (retinopathy, nephropathy),
- 3) Maternal and fetal outcomes (eclampsia/pre-eclampsia, live birth rates, birth weight, neonatal hypoglycemia, and other similar measures).

Introduction:

Among the US population, 29.1 million people (9.3%) have diabetes (1). Pre-existing diabetes has to be managed very carefully throughout pregnancy to optimize maternal and fetal outcomes (2). Among women

with T1DM who are pregnant, the tools that we have to regulate maternal glucose control include multiple daily injections (MDI), continuous subcutaneous insulin infusion therapy (CSII) also known as insulin pump therapy, and for high-risk individuals continuous glucose monitoring (CGM) (2). CGM use in pregnancy has been shown to be safe, to reduce the frequency of severe hypoglycemia, and to improve A1C values (3-6). Sensor-augmented pump therapy with CGM use continuously was shown to lower A1C more than intermittent use in pregnant women with T1DM (7). However, few studies have measured changes in glucose variability that occur with CGM use during pregnancy and no studies have evaluated how tools that allow family and friends (followers) to access glucose trends affect outcomes during pregnancy.

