During this visit, pregnant subjects will receive a physical exam, vitals, medical history, demographics, and concomitant medications. Laboratory tests will be performed to assess for A1C. SMBG values will be downloaded. If applicable CGM units and insulin pumps will be downloaded.

Stratification, Visit 2 (Week 1):

Subjects enrolled in the study from pre-conception will be asked to come to clinic as soon as a home pregnancy test or serum blood test confirms pregnancy, during which time routine clinical care will be provided and subjects will be stratified to 1 of 3 study arms based on subject characteristics. Subjects who did not have a pre-conception counseling visit who come to clinic for routine clinical care before 13 weeks of gestation will combine Visit 1 (screening) with Visit 2 (stratification with CGM start). A urine pregnancy test will be administered to confirm pregnancy. Per routine clinical care, we will screen for diabetic neuropathy on physical exam, thyroid disease (TSH blood draw), and kidney disease (24-hour urine protein with creatinine). These tests will be repeated once each trimester. Also per routine clinical care, women will be asked to get a dilated retinal eye exam each trimester and to provide the BDC with a copy of the provider's report of each exam.

Women stratified to Groups 1 and 2 who own a Dexcom G4 or G5 Platinum CGM® will be given 4 sensors. Women stratified to Groups 1 and 2 who do not own a Dexcom G4 or G5 Platinum CGM® will be given Dexcom G4 CGM units, transmitters, and 4 sensors. They will also receive training in the insertion of sensors and CGM use. A Dexcom G4 Platinum® CGM sensor will be inserted that day and will be worn in 7 day periods throughout the study. Although subjects will be asked to wear the device 7 days/week, satisfactory data capture rate is regarded as 5 days of successful CGM readings. The CGM data will be unblinded (real-time use) such that subjects will be able to view glucose values and trends, as well as receive alerts for low and high sensor glucose values. Women will be asked to check SMBG at least 7 times daily (fasting, before meals, 2 hours after a meals, and at bedtime) for the duration of the study.

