The primary endpoints are glucose variability and changes detected by hypoglycemic fear survey. We will measure indices of glucose variability (mean glucose \pm SD, % of glucose within/above/below target ranges, J Index, High Blood Glucose Index [HBGI], Low Blood Glucose Index [LBGI], Mean Amplitude of Glycemic Excursions [MAGE], CONGA_n) throughout pregnancy using the SMBG 7-point profiles for one week taken once per trimester. Hypoglycemic fear survey results will be assessed once monthly over the pregnancy. We will compare outcomes within individuals over time and between individuals of the different study arms. We will test whether outcomes differ between women using Dexcom alone and women using Dexcom with Share™ using interaction terms, and will stratify analyses if differences by group are greater than 10 mg/dL in mean glucose levels are detected. Since SMBG logs will be taken at multiple time points over the pregnancy and since CGMs will be worn continuously for the duration of each pregnancy, linear mixed models will be used to assess changes in outcome measures (GV, time spent in target below or above target) over time in each trimester of pregnancy. We will use linear mixed models to assess changes in the hypoglycemic fear survey in each month of the pregnancy. Secondary endpoints include A1C differences among study arms. Improvement in glycemic variability parameters with a possible reduction of A1C by 0.3%, measured as the difference of the mean A1C laboratory values of the arms of the study between baseline (0-3 months, first trimester), second trimester (3-6 months), and third trimester (6 to 9 months). Mixed models account for missing data, allow for an unstructured covariance matrix for repeated measures, and account for inter-subjects correlation of measurements. Secondary outcomes will be used

in the same mixed models. Differences in frequency of low alert glucose rates, high alert glucose rates, and interventions for low or high glucose values among the followers for each study arm will be analyzed with student t-tests. A p-value < 0.05 will be considered significant, and we will perform statistical analyses with SAS software (version 9.3, SAS Institute, Cary NC).

Publication Strategy:

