The BDC is a leading clinical T1DM clinical and research center. All study personnel will attend an investigator's meeting, which will be organized and conducted before trial initiation. All subjects will sign an informed consent form approved by Western Institutional Review Board (WIRB) and the Colorado Multiple Institutional Review Board (COMIRB).

Study results will be presented at national and international conferences including the Scientific Sessions of the American Diabetes Association (ADA), EASD, ATTD, etc. The Principal Investigator may submit study results for publishing to peer reviewed scientific journals, particularly within the fields of diabetes and endocrinology.

Table 1: Study Procedures for Subjects

Visit	1	2	3 - 13	14
Study Week	0	1	5-40	44-52
Informed Consent and Eligibility Criteria	X			
Demographic Data, Medical History	X			
Concomitant Medications	X	X	X	X
Adverse Events	X	X	X	X
Physical Exam	X	X	X*	X
Urine Pregnancy Test		X		
A1C	X	X	X	X
Vital Signs, Height, Weight	X	X	X	X
Record Basal, Bolus, Total Insulin Dose**	X	X	X	X
SMBG Questionnaire		X	X*	X
Glucose Meter Download	X	X	X	X
Insulin Pump Download (if applicable)	X	X	X	X
Dexcom™ CGM Training and Education (if needed, Groups 1 & 2)		X		
CGM sensor insertion		X	X	
CGM Removal/ Download		X	X	X
Record interventions of a 3 rd party for a subject's high or low glucose levels		X	X	X
Hypoglycemic Fear Questionnaire		X	X*	X
BDC Pregnancy CGM Post-Partum Questionnaire				X

* Once per trimester.

[figure not shown]
** From insulin pump download or record of patient's MDI insulin use.

Table 2: Study Procedures for Followers

Visit	1	2	3 - 13	14
Study Week	0	1	5-40	44-52
Informed Consent and Eligibility Criteria	X			
Follower Questionnaire			X*	X

* Once per month.

Figure 1 Study design:

*Visit 1 will apply for women screened at a pre-conception counseling visit. Women screened in the 1st trimester may combine visits 1 and 2.

**Visits 3 through 13 for pregnancy care and study follow-up.

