Appendix D

SMBG (Self-Monitoring Blood Glucose) Questionnaire

Subject ID: _____

Clinic Visit: (dd/mmm/yyyy) : _____ / _____ / _____

Gestational Age: 8 to 12 weeks 20 to 24 weeks 32 to 36 weeks Post-Partum

DAY	DATE	TIME POINT	BLOOD GLUCOSE BEFORE MEAL (OR BEDTIME)	SHORT-ACTING INSULIN DOSE (UNITS)	BLOOD GLUCOSE 2 HOURS AFTER MEAL
1		Breakfast			
		Lunch			
		Dinner			
		Bedtime			
2		Breakfast			
		Lunch			
		Dinner			
		Bedtime			
3		Breakfast			
		Lunch			
		Dinner			
		Bedtime			
4		Breakfast			
		Lunch			
		Dinner			
		Bedtime			
5		Breakfast			
		Lunch			
		Dinner			
		Bedtime			
6		Breakfast			
		Lunch			
		Dinner			
		Bedtime			
7		Breakfast			
		Lunch			
		Dinner			
		Bedtime			

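### The SAP names no pre-CGM baseline for glucose variability, so change in new CGM users is largely change on CGM and self-selected arms are compared without adjustment for starting variability

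*Combined protocol and SAP*

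**What the plan says.** **Endpoint and model.** The Statistical Analysis Plan measures the variability indices "throughout pregnancy using the SMBG 7-point profiles for one week taken once per trimester" and fits linear mixed models for change across trimesters. It plans comparisons within women over time and between arms. It names no baseline term and no adjustment covariate for variability. The only baseline it defines, for A1C, is the first trimester. The list of primary outcomes at the front is wider: variability is to come "from self-monitoring blood glucose (SMBG) data through log books and downloads as well as CGM downloads".

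**Timing of the log.** In Table 1 the row "SMBG Questionnaire" is blank at Visit 1, marked at Visit 2, marked once per trimester over Visits 3 to 13, and marked at Visit 14. The Appendix D form offers these windows: "Gestational Age: 8 to 12 weeks 20 to 24 weeks 32 to 36 weeks Post-Partum". It has no baseline or pre-conception box, whereas the fear survey in Appendix C has a baseline box.

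**Timing of the sensor.** The Visit 2 section states: "A Dexcom G4 Platinum® CGM sensor will be inserted that day and will be worn in 7 day periods throughout the study". The readings are unblinded. The opening summary agrees: "subjects in Groups 1 and 2 will wear the Dexcom G4 Platinum® CGM system from the first pregnancy visit until delivery". For women without a pre-conception visit, screening and CGM start fall on the same day.

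**Data from before the sensor.** The Visit 1 section states: "SMBG values will be downloaded. If applicable CGM units and insulin pumps will be downloaded". Table 1 marks a meter download at every visit. For women seen earlier at the centre, the Visit 2 section adds a chart review that includes meter and CGM downloads from the last pre-conception visit and from visits in the current pregnancy. The Control Arm section lists meter downloads for the chart-review controls. None of these is given a baseline role.

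**The concern.** Women enter an arm because they are willing, or unwilling, to wear CGM and because of the devices that they and their followers own. Starting variability may well differ between such groups. Without a value from before CGM in the model, a group that was steadier beforehand cannot be told apart from a group that CGM made steadier.

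Within Groups 1 and 2 there is a second problem. If CGM acts early, part of its effect is already in the first-trimester log, and the modelled change over trimesters understates it. The other primary endpoint, hypoglycemia fear, has a baseline form; this one does not. The results are tested at p < 0.05 and are meant to inform a larger study, so pilot status does not make the issue moot.

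**Working it through.** The plan gives no figure on this point. Its only sample-size arithmetic, 40 × (1 − 0.20) = 32 completers, reproduces and is not affected.

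**1. Count of scheduled measurements before the sensor (Table 1).** First sensor insertion: Visit 2. Seven-point logs scheduled at an earlier visit: 0. Meter downloads scheduled at an earlier visit: 1, at Visit 1. Where Visits 1 and 2 are combined, that download falls on the insertion day but can still cover earlier readings.

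**2. Women affected.** The protocol anticipates 10 in Group 1 and 20 in Group 2, so 10 + 20 = 30. This is an upper limit for new users, because both groups admit women already on CGM.

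**3. Weeks on CGM at the first-trimester log.** Let g be the gestational week at Visit 2, with CGM starting that day. For the 8 to 12 week window, the shortest exposure is max(8, g) − g and the longest is 12 − g.

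| g | Weeks on CGM |
|---|---|
| 4 | 4 to 8 |
| 5 | 3 to 7 |
| 6 | 2 to 6 |
| 8 | 0 to 4 |
| 10 | 0 to 2 |
| 12 | 0 |
| 13 | window closed |

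The range is about 0 to 8 weeks. Starting at week 4 is an assumption, and the documents give no distribution of entry weeks. At week 13, still eligible, the form has no matching box, but Table 1 marks a log at Visit 2 all the same.

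**4. What the within-arm change would show.** Suppose a fraction f of the CGM effect is present at the first log and all of it by the third trimester. First-to-third-trimester change then shows 1 − f of the effect: 100% at f = 0, 75% at 0.25, 50% at 0.5, 25% at 0.75 and 0% at 1. The documents give no value for f.

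**5. What a baseline covariate might gain in precision.** If the baseline has correlation r with the follow-up value, adjustment removes about r² of the between-woman variance: 0.5² = 25%, and 0.7² = 49%. Both values of r are assumptions only.

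**The case against.** **The data exist.** A reader might infer that the trial has no pre-CGM glucose data at all. The documents do not support that. Meter downloads are taken at Visits 1 and 2 and abstracted from earlier visits, and the outcome list counts downloads as a source for this endpoint. This objection stands, and it places the defect in the SAP, which leaves the data unused, rather than in the visit schedule.

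**The objective can still be addressed.** A reader might infer that the trial cannot answer its variability question. That goes too far. The SAP also compares arms, including one without CGM. That contrast needs no within-woman baseline, and change in Group 3 is not change on CGM. What remains is confounding. The protocol admits that the study is not randomized, but admitting this does not adjust for it.

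**The delay may be short.** It is zero for entry at week 12 and at most 4 weeks for entry at week 8. It would also be wrong to say that a woman entering at week 13 has no log until 20 to 24 weeks, because Table 1 schedules one at Visit 2. Nor does Table 1 say whether the Visit 2 form covers the week before or after the visit. A pre-insertion week is therefore possible for women with separate Visits 1 and 2, though it is not planned.

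**Some women have no pre-CGM period.** Women already on Dexcom are enrolled, and users of other CGM devices go to Group 1. Their readings before Visit 2 are on CGM, and adjusting for them could remove part of the effect. This stands and must shape the repair.

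**Adjustment is imperfect.** A noisy baseline leaves residual confounding, and it does not deal with self-selection on other factors. This also stands.

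**Conclusion.** The point holds in limited form. No 7-point log is planned before the sensor-insertion visit, and the SAP names no pre-CGM value as baseline or covariate. For new CGM users in Groups 1 and 2, at most about 30 women, the modelled change across trimesters is largely change on CGM, with about 0 to 8 weeks of wear at the 8 to 12 week log. The between-arm comparison remains available, but it does not allow for starting variability in groups that selected themselves.

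The 0 to 8 week range assumes CGM start at Visit 2 and entry between weeks 4 and 12. The size of any resulting bias cannot be computed, because the documents give neither the speed of the CGM effect nor the starting variability by arm. No sample-size figure changes.

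**What to change.** In the SAP:

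1. Define baseline as the indices computable from meter readings (mean, SD, % in range, LBGI, HBGI) in a fixed window, for example 14 days, ending before the Visit 2 sensor insertion. For prospective no-CGM women and chart-review controls, use the same length of window before the first pregnancy visit.
2. Enter the matching baseline index as a covariate in each variability mixed model.
3. Treat the first-trimester log as an on-treatment value in the CGM arms, and state whether the Visit 2 form covers the week before or after the visit.
4. Flag women using CGM at entry, which Appendix B records, and analyse them separately or in a sensitivity analysis.
5. State how a missing baseline is handled. Mixed models cope with missing outcomes, not with missing covariates.

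A paper log handed out at a pre-conception Visit 1 is not a good main repair: it could be months old by conception and would mix the effect of pregnancy with that of CGM.

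**Cost:** SAP wording and one derived baseline set from downloads already collected, with no change to CGM start. **Downsides to state:** pre-study meter checks are irregular and noisy; some baselines will be missing; any pre-conception readings used carry the effect of pregnancy as well; and adjustment reduces confounding without removing it.

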per month). Subjects already using a Dexcom G4 or G5 CGM will be provided only with the sensors. Replacement transmitters will be provided on an as needed basis during the study. A designated CDE or nurse will train each subject in the use of CGM at Visit 2, including how to use the sensor data (rate of change of glucose, to cross-check with fingerstick blood glucose as per FDA label before action is taken). Subjects in Group 2 will be additionally instructed on how to use the Platinum System with Share™ and will set up contact lists with family and friends at that visit. Subjects will be asked to wear the CGM for the duration of the pregnancy and to change sensor sites every 7 days. All subjects will be encouraged to check the blood glucose level (SMBG) before taking action on the CGM glucose values (as per the FDA label). Subjects in Groups 1 through 3 will be asked to designate a main follower who is willing to sign informed consent and fill out a questionnaire once a month.

Subjects will be asked to return to clinic a minimum of once per month for pregnancy care with a BDC provider and to receive the next month's sensors from a designated PRA. There are women whom we ask to return to clinic based on their clinical needs every week or every 2 weeks for pregnancy care who will be allowed to pick up sensors on a biweekly basis rather than monthly, if preferred. If a patient misses an appointment and needs to pick up sensors, she will be asked to reschedule her pregnancy visit and will be allowed to pick up sensors from the PRA for one more month. All subjects will be allowed to keep the devices used in the study upon completion.

The final study visit will occur in conjunction with the post-partum visit.

What is the schedule of events for the follower group?

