Women in Group 2 will be trained in the use of the Share™ technology. They will be asked to designate a main follower and up to 4 additional followers who will receive access to sensor glucose data remotely through the secure, wireless communication system. Recommendations will be made for low and high glucose sensor alerts that will be individualized to each subject's needs (for example a low glucose alert with a higher glucose value for subjects with hypoglycemia unawareness compared to those without it). The main follower for each subject will be approached and asked to sign informed consent at Visit 2 or within 2 months of the subject's first pregnancy visit. Study participation of a main follower will be encouraged but not obligatory.

Women unwilling to wear a CGM but willing to participate in the study (Group 3) will be asked to check SMBG at least 7 times daily (fasting, before each meal, and 2 hours after meals, and at bedtime), per standard of care, for the duration of the study. All 3 groups will receive education about diabetes during pregnancy.

Women in Groups 1 and 3 will be asked to designate a main follower who will not receive data through a device, but rather through contact with the subject. The main follower for each subject (Groups 1 through 3)

will be approached and asked to sign informed consent at Visit 2 or within 2 months of the subject's first pregnancy visit. Study participation of a main follower will be encouraged but not obligatory.

Data on all subjects for medical history, existing diabetes complications, medications, vital signs, height/weight, A1C (current and most-immediately pre-conception), insulin doses, glucometer downloads, insulin pump downloads (if applicable), CGM downloads (if applicable), and adverse events (AEs) will be collected. If the woman was seen at the Barbara Davis Center prior to the consent visit, we will do a retrospective chart review for medications, vital signs, height/weight, A1C, insulin doses, glucometer downloads, insulin pump downloads (if applicable), and CGM downloads (if applicable) for the most-immediate pre-conception clinic visit and for visits during the current pregnancy. Each subject will be given a hypoglycemic fear questionnaire. We will ask women about interventions that have taken place over the last month for extremely low and high glucose values, directed by patient or a third party, and keep the information on research source documents.

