Visits 3 through 13 (Weeks 5 to 40):

Subjects will come to the BDC for routine clinical care at least once per month for the duration of the pregnancy (through gestational week 40, though some women deliver up to 42 weeks gestation) and for continued study participation. Per routine clinical care, we will screen for diabetic neuropathy on physical exam, thyroid disease (TSH blood draw), and kidney disease (24-hour urine protein with creatinine) at least once each trimester. Also per routine clinical care, women will be asked to get a dilated retinal eye exam each trimester and to provide the BDC with a copy of the provider's report of each exam.

Subjects in Groups 1 and 2 will receive 4 new sensors per month, but may choose to get 2 sensors twice a month instead, at study visits. Use of acetaminophen-containing medications like Tylenol® during sensor wear may affect device performance, therefore we will ask subjects to keep a log of each time these medications are used. We will ask subjects at each monthly visit whether she used acetaminophen-containing medications during the previous month and when. Followers will be administered a brief questionnaire at the beginning of every month inquiring on the frequency of low alerts, high alerts, viewing glucose trends, and actions they may have taken on behalf of the subjects because of the above (see Table 2 and *Follower Questionnaire* for details). On source documents, we will also record how often subjects required an intervention for low or high glucose values within the previous month, and the nature of the interventions. If in Group 2, we will keep source documentation about interventions resulting from a Share™ alert within the previous month.

Data on all pregnant subjects for medications, vital signs, height/weight, insulin doses, glucometer downloads, insulin pump downloads (if applicable), and CGM downloads (if applicable) will be collected at least once per month and as often as every week. All subjects will be asked to collect a 7-point profile for SMBG measurements (blood glucose measurements before meals, 2 hours after meals, and at bedtime) along with meal insulin dosing for 1 week once per trimester (see SMBG Questionnaire). A1C will be measured once per month. Subjects will be asked about updated concomitant drugs and any AEs that may have occurred. Each subject will be given a hypoglycemic fear questionnaire.

Visit 14 (Weeks 44 to 52):

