All subjects will have routine post-partum clinical care between 4 and 6 weeks post-partum. However, a post-partum visit up to 12 weeks post-partum will be accepted as a final study visit. Data on all subjects for medications, vital signs, height/weight, insulin doses, SMBG values, glucometer downloads, insulin pump downloads (if applicable), and CGM downloads (if applicable) will be collected. All subjects will be asked to

collect a 7-point profile for SMBG measurements (blood glucose measurements before meals, 2 hours after meals, and at bedtime) along with meal insulin dosing for 1 week in the post-partum period (see SMBG Questionnaire). A1C will be measured. Subjects will be asked about updated concomitant drugs and any AEs that may have occurred. Subjects in Groups 1 and 2 may have had a Dexcom G4 Platinum CGM® for personal use prior to study participation and may thereafter still wear the device after labor and delivery. In such cases, CGM downloads will be included in study data. On source documents, we will record how often subjects required an intervention for low or high glucose values within the previous month, and the nature of the interventions. Subjects will be administered a questionnaire inquiring about the labor and delivery process, maternal and fetal complications before and after delivery, baby's anthropometrics at birth (weight and length), baby's current age, breastfeeding, and other measures (see *BDC Pregnancy CGM Post-Partum Questionnaire* for details). If the pregnancy ended early (for example, spontaneous abortion or stillbirth) or resulted in fetal or neonatal death (for example, stillbirth) we will obtain data about these outcomes. Each subject will be given a hypoglycemic fear questionnaire. Followers will be asked to fill out their last *Follower Questionnaire* during the post-partum period.

Control Arm:

As outlined in the proposal, the subjects prospectively enrolled in this arm (Group 3) will receive the same care as in the intervention arms (Groups 1 and 2) with the exception of not having access to the Dexcom G4 Platinum CGM® with or without Share™ technology.

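### The follower comparison has no measure taken before Share starts and no adjustment, so it cannot separate prior follower involvement from a Share effect on interventions

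*Combined protocol and SAP*

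**What the plan says.** **Start and end of Share.** The opening summary states: "All subjects in Group 2 will also use the Share™ technology from the first pregnancy visit until delivery". The treatment-group schedule has Group 2 women trained at Visit 2, where they "will set up contact lists with family and friends at that visit".

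**Follower form.** Under Visits 3 through 13: "Followers will be administered a brief questionnaire at the beginning of every month". In "Table 2: Study Procedures for Followers" the questionnaire is marked at Visits 3-13 (monthly) and Visit 14, with nothing at Visit 1 or 2. The Visit 14 section adds "Followers will be asked to fill out their last" form in the post-partum period. The form (Appendix E) asks only about the current month. The main follower may consent up to two months after the woman's first pregnancy visit, so the first form can come later still.

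**Group membership.** Under the recruitment heading, a CGM user goes to Group 2 if she has an Apple device and her main follower has a compatible one; otherwise she goes to Group 1. Women who decline CGM form Group 3.

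**Analysis.** The Statistical Analysis Plan says that alert rates and "interventions for low or high glucose values among the followers for each study arm will be analyzed with student t-tests". It names no baseline or covariate for this comparison. Secondary objective 1 concerns whether Share use by followers leads to interventions.

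**Related data already planned.** At Visit 2: "We will ask women about interventions that have taken place over the last month for extremely low and high glucose values", whether directed by the woman herself or by a third party. Table 1 also marks third-party interventions at Visit 2. Under Visits 3 through 13, Group 2 source documents record interventions that resulted from a Share alert.

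**The concern.** A Group 2 woman needs a main follower with a suitable device, so arm membership depends partly on a characteristic of the follower. Followers in the three arms may therefore differ, before Share starts, in how often they step in. A between-arm t-test on forms completed only after that point estimates the sum of any Share effect and any carried-over difference, and nothing on the follower form allows the two to be split.

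The rest of the plan does take starting values: the hypoglycemia fear survey is given at Visit 2 and A1C is measured at baseline. The follower form is the exception, and a start value cannot be recovered reliably once Share is running.

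A second, smaller issue is the post-partum form, which falls after the planned end of Share at delivery. The SAP does not say whether it enters the t-tests. If it does, the comparison mixes months of planned Share use with a month in which some women have stopped and others may not have.

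At stake is the follower signal that this pilot is meant to pass on to a larger study.

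**Working it through.** **Inputs from the documents**
- Anticipated groups: 10 / 20 / 10 (How many subjects per treatment arm?), summing to 40.
- Dropout 20% (SAP): 40 × (1 − 0.20) = 32 completers. The plan's figure is reproduced.
- The same rate in each arm gives Group 2: 20 × 0.8 = 16; Group 1: 10 × 0.8 = 8. Equal dropout and one participating follower per completing woman are my assumptions.
- Significance level 0.05 (SAP); two-sided is assumed because the plan does not say.
- There is no power figure to reproduce.

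**Assumptions not in the documents**
- d: prior difference in follower involvement in favour of Group 2, 0.5 to 1.0 SD.
- r: correlation between prior and on-study involvement, 0.3 to 0.7.
- True Share effect: zero.

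**Step 1: timing.** Share set-up is at Visit 2 (Week 1). The first follower form is at Visit 3 (Week 5) or later, and the last is post-partum. No form precedes Share.

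**Step 2: bias of the unadjusted comparison.** If the prior difference carries over by regression to the mean, the expected between-arm difference with no Share effect is d × r. Smallest: 0.5 × 0.3 = 0.15 SD. Largest: 1.0 × 0.7 = 0.70 SD.

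**Step 3: rejection rate.** SE = sqrt(1/16 + 1/8) = 0.433 SD, df = 16 + 8 − 2 = 22. The noncentrality is (d × r)/0.433, and the two-sided rejection rate comes from the noncentral t.

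| d | r | shift (SD) | noncentrality | rejects |
|---|---|---|---|---|
| 0 | any | 0 | 0 | 5.0% |
| 0.5 | 0.3 | 0.15 | 0.346 | 6.3% |
| 0.5 | 0.5 | 0.25 | 0.577 | 8.6% |
| 0.5 | 0.7 | 0.35 | 0.808 | 12.1% |
| 1.0 | 0.3 | 0.30 | 0.693 | 10.2% |
| 1.0 | 0.5 | 0.50 | 1.155 | 19.7% |
| 1.0 | 0.7 | 0.70 | 1.617 | 34.0% |

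With no dropout (20 v 10) the range is 6.6% to 41.5%. A prior difference of the same size in the other direction gives the same rejection rates with the sign reversed, and would mask a real Share effect.

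**Step 4: what a baseline covariate buys.** Residual variance falls by r²: 0.3² = 9% to 0.7² = 49%. In simulation (20,000 runs per scenario; d of 0.5, 0.8 and 1.0; r of 0.5 and 0.7) the adjusted test rejected 4.9% to 5.3% of the time. That result holds only under the Step 2 model with a baseline measured without error. If the arms instead differ by a stable amount d throughout, the unadjusted bias is d and adjustment leaves d × (1 − r): from 0.5 × 0.3 = 0.15 SD to 1.0 × 0.7 = 0.70 SD. Adjustment then helps but does not clear the bias.

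**The case against.** - **Share-alert records.** Group 2 interventions that resulted from a Share alert are documented monthly, which speaks directly to secondary objective 1 and needs no baseline. This stands as far as it goes: it helps attribution within Group 2. It does not give a starting level in any arm, so the between-arm test is no better for it.
- **No causal claim in the plan.** The SAP only tests for arm differences, and the section on the study's weakness concedes that the study is not randomised. A reader might infer that the plan commits itself to reading any arm difference as a Share effect; it does not say so. The point is that the comparison cannot support that reading.
- **The sizes are assumed.** Neither d nor r is in the documents, and nothing there says that followers who own devices help more. A reader might infer that the false-positive rate is in fact inflated to 34%. That is not supported; with d = 0 it stays at 5%.
- **A baseline is not a cure.** This stands (Step 4). The form is also coarse and ordinal, and existing Dexcom users may already have been sharing data, so a Visit 2 measure is not pre-Share for everyone.
- **The fallback is a proxy.** The woman's report has a different informant, is not specific to the main follower, and covers interventions, not alerts.
- **Post-partum Share use.** A reader might infer that the last form is always off Share and dilutes the effect by a fixed fraction. The documents do not support this: women keep the devices, prior owners may go on wearing theirs, and the SAP does not say how forms are combined.
- **Low stakes.** Follower participation is optional, the SAP says outcomes will not depend on it, and the pilot is unpowered. This lowers the priority but does not remove the point.

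**Conclusion.** The point holds at modest priority. The timing is clear from the text and Table 2, and the planned t-test on follower interventions has no means of separating prior involvement from Share. The 6% to 34% range is an illustration that rests on a prior difference of 0.5 to 1.0 SD, a correlation of 0.3 to 0.7, 16 v 8 followers and no Share effect; it is not an estimate of what will happen here. A baseline covariate would reduce the bias without necessarily removing it, and under the same correlations would cut residual variance by 9% to 49%. The concern applies to the intervention items. Alert counts are largely a direct product of Share, so baseline adjustment is not apt for them.

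**What to change.** 1. In the follower-intervention comparison, replace the unadjusted t-test with a model adjusted for the woman's Visit 2 report of third-party interventions in the previous month. It is already collected in all prospective groups; the retrospective controls have no follower data and do not enter this comparison. Leave alert counts unadjusted.
2. Where the follower consents by Visit 2, also give the Follower Questionnaire before Share set-up, worded for the month before. Record any sharing of CGM data before the study. Name one of the two baseline sources as the main covariate and use the other in a sensitivity analysis; do not mix them in one variable.
3. Limit the main comparison to the in-pregnancy forms. Report the post-partum form separately, and record whether Share was still in use.

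Cost: a mark in Table 2, one short extra form for followers who consent in time, a reworded recall period, a question on prior and post-partum sharing, a few sentences in the SAP and a little more analysis. Item 1 needs no new data.
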